2.5 Study Design

This is a phase 2-3 study with a total of 200 participants with newly-diagnosed intermediate or high-risk prostate cancer scheduled to undergo prostatectomy and lymph node dissection. Eligible participants will undergo baseline assessments at enrollment. Study participants will receive ^{68}Ga -PSMA-11 and undergo a PET/MRI. All patients will first be seen by a Stanford Cancer Institute physician (Drs [name], [name], [name] and [name]) who will refer patients if appropriate on clinical grounds to Dr [name] or his colleagues for this study. The following steps will take place.

1. After signed the informed consent document, participants will be given a copy of the signed form.
2. Participant will be asked to drink 1 to 2 glasses of water before arrival at the clinic
3. Participants will be weighed and vital signs (heart rate and blood pressure) will be recorded
4. Study personnel (eg, technologist) will verify subject identify; radiopharmaceutical identity; dose; and administration route. Participant will be injected IV with 3 to 7 mCi of ^{68}Ga -PSMA-11
5. Participant will void immediately prior to the scan

6. Approximately 50 to 100 minutes after the radiopharmaceutical IV administration, data acquisition will begin in the pelvic region and move toward the head. First, localizer MRI scans will be performed to define the table positions. After correct positioning of the spatial acquisition windows is ensured, the combined PET/MRI acquisition will be initiated with 3 to 5 table positions at a 4-min acquisition time per table position.
7. Vital signs (heart rate and blood pressure) will be recorded again at the completion of the study.
8. Participants will be dismissed.
9. Participants will be contacted at 24 to 72 hours following the scan in order to capture potential late occurring Adverse Events.

The ^{68}Ga -PSMA-11 PET/MRI may be repeated at the completion of treatment to evaluate response to therapy, if requested by the treating physician.

Objectives of the Study

Primary

- Sensitivity, specificity, positive and negative predictive value of ^{68}Ga -PSMA-11 PET/MRI for the detection of regional nodal metastases compared to pathology at radical prostatectomy on a per patient basis using nodal regional correlation.

Secondary

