5.3 Image interpretation

1. ^{68}Ga -PSMA-11 PET

PET images will initially be interpreted in random order at separate reading sessions by 3 board-certified nuclear medicine physicians. Cross-sectional MRI imaging from the PET will be available for anatomic correlate. Final reads for each patient will be interpreted as positive or negative for the presence of pelvic nodal disease, and positive or negative for the presence of osseous metastatic disease and soft tissue metastases outside of the pelvis.

Clinical Follow-up

- a. Prostatectomy: patients without evidence of PSMA-11 PET positive nodal or metastatic disease noted on imaging will undergo radical prostatectomy. If a PSMA-11 PET positive regional pelvic node is noted, the urologist will be informed of the location of the suspicious node and the patient will undergo prostatectomy with nodal dissection.
 - i. Patients with nodes seen on PSMA-11 PET without positive nodes on pathology, will be rescanned with CT or MRI to determine if the suspicious node was thought to be removed. A PSMA-11 PET may be repeated as well at the discretion of the treating physician.
- b. If sites of PSMA-11 PET positive osseous or distant metastatic lesions are noted, the urologist will be informed, and further evaluation including further imaging (bone scan; NaF PET; CT; or MRI cross-section imaging) or targeted biopsy will be performed in order to restage the patient prior to the decision regarding whether or not a prostatectomy will be performed as per the responsible surgeon and standard of clinical care.

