10.2 Determination of Sample Size and Accrual Rate

10.2.1 Sample Size and Power Estimate

The estimated sample size will be 200 patients to adequately power the primary aim. The power analysis will be based on the comparison of sensitivity between conventional imaging and PSMA-11 PET. With a power of 80% and a significance level of 0.01, a sample size of 61 patients with nodal metastases is required. The following assumptions are made:

- i. 30% of intermediate to high-risk patients have nodal metastases at prostatectomy.

- ii. 25% of patients will not undergo the planned prostatectomy. Patients that do not undergo prostatectomy will not be included in the analysis population, and will not undergo central imaging review.
- iii. Conventional imaging has a 45% detection sensitivity for nodal metastases on a per-patient basis (2).
- iv. PSMA-11 PET has a 65% detection sensitivity for nodal metastases on a per-patient basis.

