10.3.3 Analysis of Secondary Endpoints

We will report the sensitivity, specificity, positive and negative predictive value of PSMA-11 PET over all imaged regions as well as broken down by the following regions: extra-pelvic nodal metastases, visceral metastases and osseous metastases. Follow-up for extra-pelvic nodal metastases, visceral metastases and osseous metastases are defined as below:

i) Lymph nodes will be assessed by change in size. ^{68}Ga -PSMA-11 positive lymph nodes will be considered:

(1) True positive:

- If on follow-up imaging within 3 to 12 months, lymph nodes seen on CT or MRI decrease by more than 30% (for patients undergoing systemic treatment of focal therapy at this site) or increase by more than 20% in short axis diameter (with a minimum of 3 mm in change in size).

- If patients with solitary lymph node regions show a decrease of PSA by greater than 50% after targeted treatment (ie, external beam radiation) and the lymph nodes do not change in size (less than 30% decrease or less than 20% increase in short axis diameter).

(2) False positive:

- If on follow-up imaging within 3 to 12 months, sites of initial ^{68}Ga -PSMA-11 positive lymph node lesions seen on CT or MRI decrease by more than 30% without systemic therapy or focal therapy at this site.

- If ^{68}Ga -PSMA-11 positive lymph node lesions do not meet the criteria for above false positive or true positive findings.

ii) Visceral lesions (non-lymph node soft tissue or organ) will be assessed by change in size. ^{68}Ga -PSMA-11 positive visceral lesions will be considered:

(1) True positive:

- If on follow-up imaging within 3 to 12 months, visceral lesions seen on CT or MRI decrease by 30% (for patients undergoing systemic treatment of focal therapy at this site) or increase by 20% in largest diameter.

- If patients with solitary visceral metastasis show a decrease of PSA by greater than 50% after targeted treatment (ie, external beam radiation) and lesions do not change in size (less than 30% decrease or 20% increase in largest diameter).

(2) False positive:

- If on follow-up imaging within 3 to 12 months, sites of initial ⁶⁸Ga-PSMA-11 positive visceral lesions seen on CT or MRI decrease by more than 30% without systemic therapy or focal therapy at this site.

- If ⁶⁸Ga-PSMA-11 positive visceral lesions do not meet the criteria for above false positive or true positive findings.

iii) ⁶⁸Ga-PSMA-11 positive bone lesions will be considered:

(1) True positive:

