- If there was a corresponding positive sclerotic lesion on the CT portion of the ⁶⁸Ga-PSMA-11 PET.

- If there is focal uptake seen on the baseline bone scan performed within one month of ⁶⁸Ga-PSMA-11 PET.

- If there is a lesion noted on the initial MRI performed within one month of ⁶⁸Ga-PSMA-11 PET.

- If within 12 months, follow-up CT demonstrates development of sclerosis.

- If within 12 months, follow-up MRI demonstrates a new bone lesion.

- If within 12 months, follow-up bone scan demonstrates new focal uptake.

(2) False positive:

- If ⁶⁸Ga-PSMA-11 positive bone lesions do not meet the criteria for true positive findings.

iv) Histopathology correlation: for lesions that have biopsy correlation, we will use the following criteria to determine positive and negative lesions:

(1) Positive HP/Biopsy: Confirmed sites of metastatic or tumor involvement by histopathology/biopsy will be discussed with the responsible physician/surgeon.

(2) Negative Biopsy: Patients with suspected tumor recurrence on ⁶⁸Ga-PSMA-11 PET with negative histopathology/biopsy will be handled as outlined below:

(a) Lymph nodes:

- For patients undergoing nodal dissection: Patients will be rescanned with dedicated CT or MRI to determine if the suspicious ⁶⁸Ga-PSMA-11-positive node was removed.

- If ⁶⁸Ga-PSMA-11 positive lymph node is still present, a repeat biopsy can be pursued if clinically feasible and applicable, or follow-up using imaging as described above will be performed.

- If the corresponding node was removed, then this will be considered a False Positive.
- For patients undergoing needle biopsy: Images of the procedure will be reviewed to determine if the correct node was biopsied.
 - If the correct node was biopsied, then a negative biopsy will be considered a False Positive.
 - If the incorrect node was biopsied, then follow-up imaging as described above will be performed.

(b) Bone lesions: Given the high rate of false negative biopsies for osseous metastases in patients with prostate cancer, patients with negative bone biopsies of ^{68}Ga -PSMA-11 PET-positive lesions will be further evaluated:

- If pathology demonstrates an alternative diagnoses that is known to be ^{68}Ga -PSMA-11-positive (eg, renal cell carcinoma (RCC) metastases; Paget's disease), then this will be considered a False Positive.
- If pathology is indeterminate, then follow-up imaging as described above will be performed to determine if the lesion is a True Positive or False Positive.

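### The PSA-fall criterion in 10.3.3 has no defined baseline and does not exclude prostate or systemic treatment, so it can mislabel some size-stable extra-pelvic nodal and visceral lesions

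*Combined protocol and SAP*

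**What the plan says.** Section 10.3.3 classifies PET-positive extra-pelvic nodes and visceral lesions mainly by change in size. For lesions that stay stable it adds a PSA route to true positive. For nodes, i)(1): "If patients with solitary lymph node regions show a decrease of PSA by greater than 50% after targeted treatment (ie, external beam radiation"), on the condition "and the lymph nodes do not change in size (less than 30% decrease or less than 20% increase in short axis diameter"). For visceral lesions, ii)(1): "If patients with solitary visceral metastasis show a decrease of PSA by greater than 50% after targeted treatment (ie, external beam radiation"), with a matching size condition. Neither rule gives a PSA baseline or a time window. Neither says whether the prostate must already be out, or must be untreated, and neither excludes systemic therapy in the interval.

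A lesion that meets no criterion is a false positive by default. For nodes, i)(2) says this of cases where "positive lymph node lesions do not meet the criteria for above false positive or true positive findings"; ii)(2) says the same for visceral lesions. Section 10.3.3 has no non-evaluable class, whereas the primary analysis has one in 10.3.2 c) v).

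The cohort in 2.5 is men with "newly-diagnosed intermediate or high-risk prostate cancer scheduled to undergo prostatectomy and lymph node dissection". Under 5.3, item b, men with distant PET-positive lesions have further imaging or biopsy "in order to restage the patient prior to the decision regarding whether or not a prostatectomy will be performed". Section 10.2.1 assumes that "25% of patients will not undergo the planned prostatectomy", and 10.3.2 c) v)(2) foresees men with extra-pelvic nodal disease who are not operated. Section 3.2 excludes androgen deprivation only before PET and surgery.

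**The concern.** A PSA fall identifies the treated lesion as cancer only if that lesion is the source of the PSA that fell. This is reasonable when the prostate is gone and one lesion remains. In a newly diagnosed man the prostate is itself a PSA source at the time of the scan. The men in this secondary analysis are also the ones whose surgery may be reconsidered, so management of the prostate will vary among them.

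For a size-stable lesion without a biopsy, PSA is the only route to true positive. If PSA follows the prostate or systemic therapy, the label depends on how the man was managed and not on what the lesion was. The figures at stake are the secondary PPV, and the related accuracy measures, for extra-pelvic nodal and visceral disease.

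The neighbouring text suggests how the rule came to be here. The biopsy rules in 10.3.3 iv) refer to "Patients with suspected tumor recurrence on" PET. Section 10.3.4 speaks of BCR patients and uses PSA strata that start at 0.2 and put everything from 5.0 upwards in one group, while 3.1 lists PSA above 10 as a risk criterion for entry. The rule appears to have been carried over from a recurrence setting.

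**Working it through.** The plan gives no figure for this rule, so there is none to reproduce. The check is algebra on assumed quantities.

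**Inputs.** From 10.3.3: the threshold (a fall above 50%) and the default class (false positive). Assumed, because the documents give no values:
- f, the share of baseline PSA made by the prostate; the lesion makes the remaining 1 − f (one lesion, no other source)
- r, the fractional fall in prostate PSA between the two values
- s, the fractional fall in lesion PSA

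**Formula.** Total fall = f·r + (1 − f)·s. The rule is met if this exceeds 0.5.

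**Case 1, benign lesion.** The lesion makes no PSA, so f = 1 and the fall equals r. If treatment of the prostate or systemic therapy lowers PSA by 90% (r = 0.9), the fall is 90% and the benign lesion is a true positive. Any r above 0.5 does the same.

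**Case 2, real metastasis fully treated, prostate present and untreated.** With s = 1 and r = 0 the fall is 1 − f:
- f = 0.25: 75%, rule met
- f = 0.50: 50%, not met, because the rule needs more than 50%
- f = 0.75: 25%, not met
- f = 0.90: 10%, not met

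So if the metastasis made half or less of the PSA, even complete response cannot satisfy the rule. If it is stable in size and unbiopsied, the default line makes it a false positive. With s below 1 the fall is smaller still.

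**Case 3, prostate already removed, post-operative baseline.** With f = 0 the fall equals s. PSA follows the lesion and the rule does what it is meant to do.

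**Case 4, prostate and lesion both treated.** With r = s = 0.9 the fall is 90% at every f. Benign and malignant lesions pass alike, so the criterion no longer separates them.

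**Effect on PPV among the lesions decided by this rule.** Let m be the true malignant share, a the share of benign lesions with a PSA fall from other treatment, and b the share of metastases without the fall. Observed PPV = m(1 − b) + (1 − m)a.

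| m (true PPV) | a = 0.5, b = 0 | a = 0, b = 0.5 | a = b = 0.5 |
|---|---|---|---|
| 0.30 | 0.65 | 0.15 | 0.50 |
| 0.50 | 0.75 | 0.25 | 0.50 |
| 0.70 | 0.85 | 0.35 | 0.50 |

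For m = 0.5, for example: 0.5 × 1 + 0.5 × 0.5 = 0.75, and 0.5 × 0.5 + 0.5 × 0 = 0.25. The error can go either way. In the last column the PPV is 0.50 whatever the truth.

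**How many lesions.** The plan's assumption gives 200 × 0.25 = 50 men not operated. That is not a count of affected men. The documents do not say how many of the 50 have a distant PET-positive lesion, and operated men can also be affected if the PSA baseline precedes surgery or systemic therapy intervenes.

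**The case against.** The natural reading of a fall after targeted treatment compares PSA just before that treatment with PSA just after it. For a man operated first, the earlier value is then post-operative and the rule works; the plan expects 75% of men to be operated. This stands, and it limits the fault: the text does not require that baseline, and it does not deal with men who keep the prostate or receive systemic therapy in the interval. The operated share may also be lower among men with distant lesions.

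A real metastasis in case 2 becomes a false positive through the default line. The PSA rule merely fails to rescue it, and without that rule more stable metastases would fall there. This stands too, and it is why the default lines have to be amended along with the PSA rule.

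The affected set is narrow: solitary, stable in size, given targeted treatment, unbiopsied, and nodal or visceral. Section 5.3 provides for targeted biopsy, and biopsied lesions follow 10.3.3 iv). This also stands.

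A reader might infer that the rule is known to have been written for men without a prostate. No section states its origin; the recurrence wording supports an inference only. A reader might also infer that the secondary PPV as a whole measures treatment of the primary tumour. The documents do not support that, because size change and biopsy decide other lesions and case 3 is sound.

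**Conclusion.** The concern holds in a limited form. As written, the PSA criterion can make a benign lesion a true positive when prostate or systemic treatment lowers PSA. Together with the default line, it can also leave a treated metastasis as a false positive when the untreated prostate makes half or more of the PSA. Among lesions decided by this rule, the shift in PPV can be large in either direction: 25 percentage points up or down at m = 0.5 in the first two columns of the table. Those values rest on assumed m, a and b. The effect on the reported secondary PPV depends on a number of lesions that the documents do not allow one to estimate.

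The point does not reach the primary endpoint. Its follow-up rule in 10.3.2 c) uses biopsy or size change without PSA, and the success criteria concern regional nodes only. Bone lesions have no PSA criterion. The change should be made because it is cheap and removes an ambiguity that could decide individual classifications; the trial's main conclusion does not hang on it.

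**What to change.** Change the classification text only; nothing here bears on how any man is treated.

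1. In 10.3.3 i)(1) and ii)(1), count the PSA criterion only when the baseline is the last PSA after prostatectomy and before the targeted treatment, with no systemic therapy and no other treatment of the prostate or prostate bed between the two values.
2. In the default lines of i)(2) and ii)(2), class as non-evaluable any size-stable, unbiopsied lesion that received targeted treatment but for which that condition does not hold. The primary analysis already has such a class in 10.3.2 c) v). A lesion for which the condition holds but PSA does not fall by more than 50% stays under the existing default.
3. Report PPV three ways: without the non-evaluable lesions, with all of them counted as true positives, and with all counted as false positives. State their number.

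The cost is a few sentences plus PSA values and treatment dates. The study calendar in section 7 lists no PSA measurement, so these are assumed to be available from routine care. The PPV denominator becomes smaller, and the exclusions will be concentrated in men not operated, who matter for this endpoint and whose management may follow from the PET result. The two-way count makes that loss visible but does not recover the missing information.

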Another way to evaluate the skeleton using PET technology is with ^{18}F sodium fluoride (^{18}F -NaF). In fact, bone scintigraphy with ^{18}F was performed prior to introduction of $^{99\text{m}}\text{Tc}$ based agents, achieving excellent quality studies (15, 16). ^{18}F is an avid bone seeker, a property due to the fact that it is an analogue of the hydroxyl group found in the hydroxyapatite bone crystals. ^{18}F has the desirable characteristics of high and rapid bone uptake accompanied by very rapid blood clearance, which results in a high bone-to-background ratio in a short time. High-quality images of the skeleton can be obtained less than an hour after the intravenous administration of ^{18}F . ^{18}F is a positron emitter, allowing for PET imaging. Thus, imaging skeletal lesions with ^{18}F -PET/CT appears as a logical approach for acquisition of highly sensitive and specific images. The lack of

reimbursement and the high costs of ^{18}F currently prevent its clinical utilization, but ^{18}F -PET/CT was proved to be superior in bone lesion detection $^{99\text{m}}\text{Tc}$ MDP bone scan and SPECT in patients with prostate cancer.

However, at initial staging the issue is detection of pelvic and retroperitoneal small lymph node metastases that don't trigger size criteria on CT and MRI; bone metastases are a rare presentation.

Other tracers, such as ^{18}F - or ^{11}C -labeled choline and [^{11}C]-acetate, are used mainly for the diagnosis of recurrent (17-19) or metastatic (20) prostate cancer. Their feasibility in primary diagnosis is limited because of uptake in benign tissue such as benign prostatic hyperplasia or inflammatory lymph nodes (21, 22).

Although choline-based PET/CT is widely used outside the US for imaging prostate cancer, there have been numerous studies reporting a low sensitivity and specificity, especially at low prostate specific antigen (PSA) levels (23, 24). Consequently, improved imaging of prostate cancer is necessary. One novel promising method is PET imaging with ^{18}F -FACBC, a new synthetic amino acid. Recent evaluations by Nanni, *et al.* indicate that this tracer might be superior when compared to choline PET/CT (25). However, recent work indicates that ^{18}F -FACBC uptake in prostate cancer is similar to that in BPH nodules (26).

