5.2 Details of Imaging (ie, dynamic, static, number of scans, etc)

A localizer MRI scan will be performed at 45 minutes after injection of 3 to 7 mCi of ^{68}Ga -PSMA-11 to define the table positions. After correct positioning of the spatial acquisition windows is ensured, the combined PET/MRI acquisition will be initiated with 3 to 5 table positions at a 4-min acquisition time per table position. A volumetric T1 acquisition with fat-water separation and motion correction to enable free-breathing will be obtained at each table position and used for the generation of attenuation maps and for

anatomic allocation of the PET results. Simultaneously with the start of the T1 MRI sequence, the PET acquisition will start at the same table position, thus ensuring optimal temporal and regional correspondence between MRI and PET data. The PET acquisition time will be 4 min per table position, taking delayed acquisition times and radioactive decay into account. As the T1 will take less than 4 minutes, a rapid diffusion weighted MRI will also be performed. After completion of the PET acquisition, the table will be moved to the next table position and the procedure will be repeated. Upon completion of the PET acquisition for all stations, volumetric post-contrast T1- and T2-weighted MR images may be obtained at multiple stations as needed.

The PET emission scan is corrected using segmented attenuation data of the MRI scan. The PET images are reconstructed with a standard iterative algorithm. All images are reformatted into axial, coronal, and sagittal views and viewed with the software provided by the manufacturer (AW, GE Medical Systems).

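### One of six bone true-positive criteria cannot be met on PET/MRI, and lesions confirmed only by already-present sclerosis on a stand-alone CT, or only by NaF PET, are scored false positive

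*Combined protocol and SAP*

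**What the plan says.** Section 5.1 names PET/MRI as the only modality. Section 5.2 confirms that attenuation correction does not use CT: "The PET emission scan is corrected using segmented attenuation data of the MRI scan". Section 8.1 attributes the whole effective dose of the scan to the tracer. Section 5.3 describes what the readers have for anatomy: "Cross-sectional MRI imaging from the PET will be available for anatomic correlate".

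When the PET shows an osseous or distant lesion, section 5.3 b says that "further evaluation including further imaging (bone scan; NaF PET; CT; or MRI cross-section imaging) or targeted biopsy will be performed" to restage the patient before the decision on surgery.

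Section 10.3.3 iii) then sets the reference standard for PSMA-positive bone lesions. Any one of six criteria makes a lesion a true positive:

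1. "If there was a corresponding positive sclerotic lesion on the CT portion of the" PSMA PET.
2. "If there is focal uptake seen on the baseline bone scan performed within one month of" the PSMA PET.
3. A lesion on the initial MRI, done within one month of the PSMA PET.
4. "If within 12 months, follow-up CT demonstrates development of sclerosis".
5. A new bone lesion on follow-up MRI within 12 months.
6. New focal uptake on a follow-up bone scan within 12 months.

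A bone lesion that meets none of these is a false positive. Lesions with a biopsy are handled under iv). Bone has no non-evaluable category. The primary nodal analysis does have one, in 10.3.2 c) v), for PET-positive nodes left in place without definitive follow-up.

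**The concern.** The bone reference standard does not match the scan being evaluated or the work-up that the protocol describes. Criterion 1 presupposes a PET/CT. Once it is set aside, CT can confirm a lesion only by showing sclerosis that was not there before, so a lesion already sclerotic at staging or restaging has no CT route. NaF PET has no route at all, although section 2.1 says that 18F PET/CT "was proved to be superior in bone lesion detection" to the 99mTc bone scan, a test that the criteria do accept.

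Because every unmatched lesion is scored false positive, this gap works in one direction: a true lesion without a listed confirmation counts as an error of the tracer. Osseous performance is a named secondary objective and is to be reported separately. Section 2.1 describes bone metastases as rare at initial staging, so the denominator will be small and each reclassified lesion will visibly move PPV.

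**Working it through.** The plan states no figure on this point, so there is none to reproduce. The check sets the criteria beside the work-up list and then works out the direction and form of the bias.

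**Step 1. Which criteria can operate.** Sections 5.1 and 5.2 describe no CT component, so criterion 1 cannot be met. Criteria 2 to 6 can. One of six is inoperable and five remain.

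**Step 2. Which 5.3 b tests can confirm a bone lesion under 10.3.3.**

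| Test in 5.3 b | True-positive route in 10.3.3 |
|---|---|
| Bone scan | Yes: baseline within one month, or new uptake within 12 months |
| MRI | Yes: initial MRI within one month, or new lesion within 12 months |
| CT | Partial: only sclerosis that develops by follow-up; none if it is already present |
| NaF PET | None |
| Targeted biopsy | Yes, under iv) |

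**Step 3. Form of the bias.** Section 10.3.3 iii) defines only true and false positives for bone, so PPV is the measure followed here, counted by lesion. Let N be the number of PSMA-positive bone lesions, p the PPV under a complete reference standard, and f the share of truly positive lesions whose only confirmation is already-present sclerosis on a stand-alone CT or NaF PET.

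- True lesions: N × p.
- Counted as true positive: N × p × (1 − f).
- Denominator: still N, because unmatched lesions stay in as false positives.
- Reported PPV = p × (1 − f); loss = p × f.

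**Step 4. Assumed values.** The documents give neither p nor f.

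| p | f | Reported PPV | Loss |
|---|---|---|---|
| 0.90 | 5% | 0.90 × 0.95 = 0.855 | 0.045 |
| 0.90 | 25% | 0.90 × 0.75 = 0.675 | 0.225 |
| 0.80 | 5% | 0.80 × 0.95 = 0.76 | 0.04 |
| 0.80 | 25% | 0.80 × 0.75 = 0.60 | 0.20 |
| any | 0% | p | 0 |

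**Step 5. What the proposed rules would do.** Take p = 0.90 and f = 25%. If all of f is already-present sclerosis on CT, accepting that finding restores 0.90. If all of f is NaF-only and those lesions become non-evaluable, with no non-metastatic lesion leaving, PPV = 0.675 / (1 − 0.225) = 0.675 / 0.775 = 0.871. Most of the loss is recovered without treating NaF uptake as proof.

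**The case against.** The strongest reply is that the gap may be nearly empty. The six criteria are alternatives, and 5.3 b joins its tests with an or. Bone scan, MRI, 12-month follow-up and biopsy all have routes, so a lesion seen on NaF PET or stand-alone CT is lost only if it meets none of them. Every scanned man also has a T1 and a diffusion-weighted MRI in the same session (section 5.2). If that examination is the initial MRI of criterion 3, it largely replaces the lost CT criterion. NaF PET may be uncommon too: section 2.1 says that cost and lack of reimbursement keep 18F out of clinical use. The success rule in 10.3.2 c) concerns regional nodes only and is untouched.

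Most of this stands and limits the size of the point. The MRI argument is unresolved. The plan does not say whether the same-session MRI is the initial MRI, and describing an MRI performed within one month of the PET reads more naturally as a separate examination. If it does count, part of the test under evaluation helps to confirm itself. Either way the plan needs a stated rule.

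Three stronger readings might be inferred and are not supported:

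- **That the bone rules depend on CT.** Criterion 1 is one of six.
- **That half of true bone lesions are lost, because two of the four imaging tests lack a full route.** This needs each lesion to have exactly one test, all four used equally, every CT-examined lesion already sclerotic, and no contribution from study MRI, follow-up or biopsy. The documents support none of these.
- **That the one-month limit for bone scan and MRI conflicts with the 90-day limit in section 3.1.** The latter is an eligibility window for CT or MRI and the former a reference-standard window; they serve different purposes.

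**Conclusion.** The point holds in a limited form. Criterion 1 is wrong as written for a PET/MRI study. Already-present sclerosis on a stand-alone CT has no true-positive route, nor does NaF PET, although 5.3 b names both tests. The catch-all rule turns the gap into a downward bias in osseous PPV of p × f.

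The size cannot be fixed from the documents. It ran from 0.04 to 0.225 over the assumed values shown, and it is zero if every such lesion also meets an MRI, bone-scan, follow-up or biopsy criterion. The result assumes lesion-level counting and a literal reading of the criteria. It touches one part of a secondary objective and not the primary success rule. It should be corrected because the inconsistency is definite and the repair is cheap.

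**What to change.** Amend 10.3.3 iii) as follows:

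- Replace criterion 1 with a corresponding sclerotic lesion on a stand-alone diagnostic CT done for staging or as part of the 5.3 b work-up.
- State whether the MRI acquired with the study PET counts as the initial MRI in criterion 3.
- Add a non-evaluable category for bone lesions whose only work-up beyond the study scan is a test with no listed criterion, such as NaF PET alone, in line with what 10.3.2 c) v) does for unresolved nodes.
- Report osseous PPV twice: with these lesions excluded, and with them kept as false positives.

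The one-month windows can stay as they are, and NaF uptake need not be accepted as proof of metastasis.

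The cost is SAP wording only, with no new imaging and no change to the work-up in 5.3 b. There are two downsides. Some benign sclerotic lesions may be accepted as true positives, which would push PPV up. A few lesions would also leave an already small denominator; reporting PPV both ways shows how much that matters.
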